## **3. Study design**

To address these objectives, we will conduct an observational cohort study in 1200 pregnant women who will be recruited at the first antenatal care (ANC) visit from the Gugulethu and one additional facility in the Hanover Park subdistrict of the Metro Region (to be identified in conjunction with provincial and local health authorities) Midwife Obstetric Units in Cape Town (n=600 pregnant women per site). We will follow the enrolled women through 12-months post-delivery.

**Setting.** The study will take place in two urban townships in Cape Town (Gugulethu and Hanover Park) with high HIV incidence that span the different socioeconomic, cultural, and ethnic groups in South Africa.

- Site 1: Gugulethu Midwife Obstetrics Unit (MOU)**
- Site 2: Hanover Park**

We selected those communities because of the high HIV prevalence there in pregnant and breastfeeding women, and because of the high number of mothers visiting every month for ANC and labour/delivery. Further, our team has several years' experience implementing research studies in those MOUs which will facilitate the integration of the study there. In 2017, Gugulethu saw over 3300 new ANC consultations per month, and 72%

(n=2300) are HIV-negative. Hanover Park has saw over 4900 new ANC consultations/month of which 87% are HIV-negative (n=4200). Considering our experience and patient flow, we are confident that at least 60 women/month per facility can be enrolled. Further, Drs. [name], [name] and colleagues have conducted research in the Gugulethu and Hanover Park communities for more than a decade and have substantial experience partnering with local health services. Building on this platform, we will use existing infrastructure in each clinic, including capacitating existing clinical providers, pharmacists and counselors, to provide PrEP care to pregnant and breastfeeding mothers. We will hire study staff to assist in the coordination, data management, and overall quality assurance of the counseling, drug provision and participation follow-up.

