#### **4. Study population**

Study counselors will enroll consecutive eligible, consenting pregnant adolescent girls ( $\geq 16$  years) and women in ANC (n=600 women per site; N=1200 pregnant women) and follow them up for 12-months postpartum or until censorship for a mean of 18-months' follow-up.

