## Adverse events:

- **Maternal adverse events:** We will collect data on maternal adverse events by asking mothers about intercurrent medical events, which will be reviewed by an obstetrician, including any hospitalizations or illnesses. We will also track and report changes in creatinine or other toxicities in women on PrEP.
- **Infant adverse events:** We will collect data on infant adverse events by asking mothers about infant health or intercurrent medical events, which will be reviewed by a pediatrician.
  - Adverse birth outcomes will include infants that were small for gestational age, pre-term births, miscarriage and stillbirths.

Table 1: PrEP-PP cohort measures by participant study month

and breastfeeding in local languages (at each visit)																
Routine ANC and postnatal care, well-baby visit follow-up (as available in standard of care), including rapid HIV testing, pregnancy, and birth outcomes	X	X	X	X	X	X	X		X		X		X			X
Survey to collect: behavioral acceptability, knowledge, and substance use data	X	X	X	X	X	X	X		X		X		X			X
Screening at enrolment for Hepatitis B and creatinine. If HBsAg+ = excluded from study; if creatinine eGFR<60, excluded from study	X															
Laboratory testing for STIs (chlamydia, gonorrhoea) & treatment if positive	X				X		X									
For women on PrEP:																
Laboratory tests of creatinine (if eGFR<60ml/min cannot continue on PrEP)	X			X												X
PrEP pharmacy refills and adherence supportive counseling monthly (for first 3 months on PrEP) then every 2 months for following months	X	X	X		X		X		X		X		X			X
Laboratory testing: renal function, hepatitis B; DBS taken for TDF-DP adherence measures (bi-monthly in participants on PrEP)	X	X	X		X		X		X		X		X			X
In-depth interviews for 30 participants per site (N=60) among 30 PrEP users and 30 non-PrEP users						X										X
Collect study data on: (1) PrEP counseling, (2) PrEP medication when requested, (3) regular appointments, (4) IEC materials, (5) adherence counselling and support by facility, through patient survey at every study visit	X	X	X	X	X	X	X	X	X	X	X	X	X	X	X	X
Vaginal swab for microbiome	X		X*													

\*between 24 and 28 weeks gestational age.

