## Sample size considerations

The projected sample size for the study is *1200 women enrolled from 1st ANC visit until 12-months postpartum (estimated mean of 18-months follow-up)*. This estimate is based on the following assumptions:

- (1) 60% of women will initiate PrEP during the study period (versus approximately 40% who will not);
- (2) Approximately 75% of women on PrEP will be retained in care at 12-months (defined as not missing >1 study visit among women on PrEP)
- (3) 70% of those retained in care (n=378) will adhere to PrEP during at-risk periods.

A sample size of 1200 women yields 80% power to detect identify a relative risk of 2.0 or greater in key covariates including age (<25 vs. >25 years), pregnancy and relationship status associated with PrEP initiation versus non-initiation. A sample size of 378 women (e.g. 70% of women retained in the study on PrEP will be adherent as measured by TDF-DP measures) yields 80% power to detect relative risks of 2.0 or greater associated with persistence in the cohort. The analysis will be based on women who complete the 12-month postpartum cohort follow up. We will use relative risk ratios performed at a two-sided  $\alpha$  level of 0.05.

## Statistical analysis considerations for AIMS 1 & 2

The primary analysis for *Aim 1* will focus on measuring the distribution of women across the PrEP cascade including: initiation, continuation and persistence. **PrEP initiation** will be based on a woman's uptake of PrEP and allow for stoppage and re-initiation; **PrEP continuation** will be defined as not missing >1 visit among those on PrEP (with separate analyses of PrEP stoppage). For **PrEP persistence** for women on PrEP we will measure both *perfect persistence* (i.e. level of objective persistence throughout pregnancy and breastfeeding periods) as well as "*prevention-effective*" persistence (i.e. persistence during times of sexual activity) in participants through objective and subjective measures to evaluate agreement between the two measures, and the level of under- or over-reporting. Primary persistence analyses will use objective measures (TDF-DP from DBS) taken on all those who enrolled and initiated PrEP; subsidiary analyses will consider (i) other persistence measures and (ii) multiple imputation for missing persistence data.

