Health outcomes and adverse events	Any side-effects, change in creatinine clearance, any negative maternal or neonatal outcomes (for mother and infant) compared by PrEP use/non-use	Electronic provider log (REDCap)	Weekly and quarterly
Infant growth outcomes	Measure infant weight, length, z-score and any adverse events in infants compared by PrEP use/non-use	Electronic provider log (REDCap)	Weekly and quarterly

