#### ***Methods/Approach:***

- (1) Study flow figure (see Continuation Flowcharts)
- (2) Number screened per week and month (target= 18 per week, 72 per month) vs number enrolled
  - a. The projected sample size for the study is 1200 women enrolled until 12-months postpartum (estimated mean of 18-months follow-up).
- (3) Subjects initiating PrEP compared to those who do not
  - a. Estimated that 60% of women (n=720) will initiate PrEP during the study period (versus approximately 40% who will not).
- (4) Continuation and persistence by group
  - a. Assumed that approximately 75% of women on PrEP (n=540) will continue on PrEP at 12-months (defined as not missing >1 study visit among women on PrEP);
  - b. Assumed that 70% of those retained in care (n=378) will adhere to PrEP during at-risk periods.
- (5) Final completion rates
  - a. Compare final number of participants who enroll in study, who initiate PrEP, who are retained in care, and who adhere to PrEP to sample sizes needed to yield 80% power (i.e., n=1200, 720, 540, 378, respectively).
- (6) Number of subjects in analysis data sets
  - a. Consider number of participants that will potentially be excluded from analyses because of withdrawal from study, missing data on key covariates or outcomes, etc.

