***Methods/Approach:***

Tabulation of adverse effects with each treatment group:

- (1) Number of events by type of event
  - Describe the frequency of any laboratory or self-reported side effects (e.g. changes in creatinine clearance, or self-reported side-effects [GI symptoms, headache, and etc]). Analyses will include pure-count and person-time approaches. Confidence intervals will be calculated following the method of Breslow and Day. We will also describe pregnancy (miscarriage, stillbirth) and infant outcomes over time (including birthweight, gestational age at delivery, pregnancy loss) by PrEP status (on/off PrEP and by persistence to PrEP)
- (2) Number of subjects by highest grade of event
- (3) Reasons for termination of treatment

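### SAP 2.6 plans person-time adverse-event rates by PrEP use without defining the at-risk woman-time or splitting it by pregnancy status, so a crude on/off rate ratio can depart from 1, in either direction, with no PrEP effect.

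*Combined protocol and SAP*

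**What the plan says.** SAP 2.6 (Adverse effects, Methods/Approach) says of laboratory and self-reported side effects: "Analyses will include pure-count and person-time approaches". The same item goes on to describe pregnancy and infant outcomes over time "by PrEP status (on/off PrEP and by persistence to PrEP". SAP Table 1 lists, under health outcomes and adverse events, side effects, change in creatinine clearance and "any negative maternal or neonatal outcomes (for mother and infant) compared by PrEP use/non-use".

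The adverse-event table shell in SAP section 4 defines PrEP use by intake in the last 30 days, so a woman can move between user and non-user. The protocol (section 5, Adverse events) collects maternal events by "asking mothers about intercurrent medical events, which will be reviewed by an obstetrician, including any hospitalizations or illnesses".

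Follow-up spans two different states. Protocol section 4 will "follow them up for 12-months postpartum or until censorship", and the SAP sample-size text gives "1200 women enrolled from 1st ANC visit until 12-months postpartum (estimated mean of 18-months follow-up").

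Nothing in SAP 2.6 names the woman-time at risk. Pregnant/postpartum appears as a subgroup in SAP 2.4 (for the cascade outcomes) and among the subgroups to consider in SAP 2.7, and pregnancy status is a main exposure in the cascade models. None of these is tied to the adverse-event rates.

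**The concern.** Some of the events collected can occur only in pregnancy, such as an obstetric admission for a pregnancy complication. Others, such as nausea and fatigue, which the protocol lists as TDF/FTC side effects, can plausibly be commoner in pregnancy whatever the woman takes. On the planned timetable about two thirds of follow-up is postpartum. PrEP is offered at the first antenatal visit and women stop or start later, so the pregnant share of on-PrEP time will in general differ from that of off-PrEP time.

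A crude on/off rate ratio then mixes any drug effect with this difference. Adjusting for baseline characteristics does not remove it, because pregnancy status changes during follow-up. Adverse events are an Aim 1 outcome in a population that the protocol itself calls vulnerable. A false signal of harm or of safety would therefore matter.

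**Working it through.** **The plan's own figures.** "Estimated that 60% of women (n=720) will initiate PrEP during the study period": 1200 × 0.60 = 720. Continuing at 12 months: 720 × 0.75 = 540. Adhering: 540 × 0.70 = 378. All three match SAP 2.2. The documents give no event rate or rate ratio for SAP 2.6, so there is no further figure to reproduce.

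**Inputs.**
- From the plan: 1200 women, 60% initiating, 75% continuing at 12 months, 18 months' mean follow-up, and 12 months postpartum ("We will follow the enrolled women through 12-months post-delivery"). Pregnant time is therefore 18 − 12 = 6 months on average.
- Assumed: all 720 start at enrolment; the 75% is an on-PrEP survival curve with exponential stopping; nobody restarts; women who stop stay observed; the event rate per pregnant month is constant and the same on and off PrEP.

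**Woman-months.** λ = −ln(0.75)/12 = 0.02397 per month.
- On PrEP, pregnant: 720 × (1 − e^(−6λ))/λ = 4,024
- On PrEP, postpartum: 720 × (e^(−6λ) − e^(−18λ))/λ = 6,502
- Off PrEP, pregnant: 1200 × 6 − 4,024 = 3,176
- Off PrEP, postpartum: 1200 × 12 − 6,502 = 7,898

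Pregnant share on PrEP: 4,024/10,526 = 38.2%. Off PrEP: 3,176/11,074 = 28.7%.

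**Ratio with no PrEP effect, if all woman-time is the denominator.** Let the postpartum rate be k times the pregnancy rate. Then RR = [s_on + k(1 − s_on)] / [s_off + k(1 − s_off)].
- k = 0: 0.3823/0.2868 = 1.33
- k = 0.25: (0.3823 + 0.1544)/(0.2868 + 0.1783) = 1.15
- k = 0.5: (0.3823 + 0.3089)/(0.2868 + 0.3566) = 1.07

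**Later starts (k = 0).** Let 25% of initiators start at delivery. On-PrEP time is 3,018 pregnant and 6,754 postpartum months; off-PrEP time is 4,182 and 7,646. The shares are 30.9% and 35.4%, and RR = 0.87.

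**Other variations (k = 0; assumptions, not plan figures).**

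| Change from the base case | RR with no effect |
|---|---|
| 10% of initiators start at delivery | 1.13 |
| About 17% start at delivery | 1.00 |
| 25% start 3 months after enrolment | 1.09 |
| 40% start 3 months after enrolment | 0.96 |
| 90% on PrEP at 12 months | 1.13 |
| 50% on PrEP at 12 months | 1.73 |
| 4 or 5 pregnant months | 1.35 or 1.34 |
| Linear decline in PrEP use | 1.35 |
| No stopping after month 12 | 1.28 |
| Stoppers leave observation, never-users stay | 1.15 |
| Stoppers leave, never-users lost at the same rate | 1.00 |

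**With the split.** Using only pregnant woman-time (4,024 on, 3,176 off), a common event rate gives a ratio of 1.00 under the same constant-rate assumption.

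**Absolute rates.** For k = 0, dividing by all woman-time understates the rate per pregnant woman-month by a factor of 1/0.3823 = 2.6 on PrEP and 1/0.2868 = 3.5 off PrEP.

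**The case against.** A reader might infer that the plan pools pregnant and postpartum time and will therefore make PrEP look about a third more harmful. The documents do not support that reading.

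- **Pooling is not stated.** SAP 2.6 leaves the denominator undefined. Its person-time sentence directly follows the side effects; pregnancy outcomes come in a later sentence that only describes them by PrEP status. This stands: the fault is an undefined denominator, not a declared wrong one.
- **Pregnancy losses are laid out as counts and percentages.** The birth-outcome shells in SAP section 4 show n and % by PrEP status, with no person-time. This stands, and dilution by postpartum time does not arise there. The adverse-event shell is also N and %, but SAP 2.6 separately promises person-time analyses with confidence intervals.
- **The full third needs a zero postpartum rate.** This stands. For side effects, where person-time is most clearly planned, 1.07 to 1.15 is the more relevant range under the same assumptions.
- **The direction is not established.** The SAP allows initiation at any time in the study, and follow-up visits offer PrEP again. The 75% is defined by missed visits, not by pills taken, and some of the remaining women will be lost. This stands. Stopping PrEP is not among the protocol's censoring reasons, however, so the plan does intend to keep women who stop under follow-up.
- **Side effects may be poorly recorded off PrEP.** Follow-up Step 5 asks women on PrEP, while the survey section collects symptoms from mothers at all visits. Any limit on off-PrEP recording is a separate weakness of the comparison and does not remove this one.
- **A pregnant/postpartum subgroup is already listed.** Applied to SAP 2.6 it would largely solve the problem, but SAP 2.7 only says to consider it and does not link it to the safety rates.

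**Conclusion.** The point holds as a gap in SAP 2.6. Person-time rates are planned for a status that varies over pregnancy and the postpartum year, with no at-risk time defined and no split by pregnancy status. If all woman-time is used, the crude on/off ratio can depart from 1 with no PrEP effect.

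The size depends on assumptions that the documents do not settle. The 1.33 figure requires all starts at enrolment, the visit-based 75% read as time on PrEP, women who stop still observed, and events that cannot occur postpartum. A modest share of starts at delivery removes or reverses it. The supportable conclusion is therefore that the ratio would partly reflect when women start and stop PrEP, in a direction that cannot be fixed in advance. It is not supportable to say that the plan inflates harm by a third or usually errs towards harm.

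**What to change.** In SAP 2.6:

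1. State the woman-time at risk for each type of event, with pregnant time ending at delivery or pregnancy loss.
2. Report adverse-event and side-effect rates separately for pregnant and postpartum woman-time, and compare on with off PrEP within each. Where one figure is needed, use a rate ratio stratified by pregnancy status.
3. For any rate of pregnancy-only events, use only pregnant woman-time or the number of pregnancies as the denominator. Where person-time is used, take gestational age as the time scale, with entry at the gestation at enrolment. This also handles risks that change over pregnancy, which a simple split does not.
4. Keep the birth-outcome shells as counts and percentages.

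The cost is a few sentences and one extra stratification. Gestational age at baseline and at delivery are already among the planned data items (SAP 2.3 and 2.6), so no new collection should be needed. The downside is fewer events per stratum and wider intervals.

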## **2.7 Subgroup analyses**

***Purpose:***

To determine if all subgroups experience similar treatment effects or if there are subgroups that behaved differently.

***Methods/Approach:***

- (2) Pre-specify subgroups that will be analyzed. Consider subgroups defined by:
  - a. Different levels of key prior exposures: STI diagnosis, age, relationship status, pregnant/postpartum

## **3. Post-hoc (data driven) analyses**

***Purpose:***

- (1) To document which analyses were conducted after the results in section 2 were known.
- (2) To document the rationale for these analyses.
- (3) To pre-specify their interpretation in the context of the primary and secondary results and their impact on the overall trial conclusions.

**Methods/Approach:**

TBD

#### 4. Table and Figure Templates

Outline tables and figures that will be produced for the analysis. This will include all analyses. Tables and figures for the paper will be constructed separately.

**Table 1. HIV risk factors associated with PrEP uptake in HIV-uninfected pregnant women (N=XXX)**

	Person time on PrEP (n=x)		Person time not on PrEP (n=y)		Crude HR (95% CI)	Adjusted HR (95% CI)
	n	%	N	%		
Age (median and IQR)						
Age <25 years						
Age >=25 years						
Primigravida						
Knew about PrEP						
Ready to start PrEP today (Agree + Strongly Agree)						
Intended to get pregnant						
Married or cohabiting						
More than 1 sex partner						
STI+ diagnosis (chlamydia, gonorrhoea, and/or trichomonas vaginalis)						
Reported depression or anxiety in pregnancy (EPDS <13 score)						
HIV+ partner						
Partner HIV status unknown						
Reported IPV in past year						
Reported alcohol/drug use in past year						

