### The objectives of the study are to:

**AIM 1:** Determine the distribution of women across the PrEP cascade (initiation, continuation and persistence on PrEP) and outcomes (maternal HIV incidence, infant HIV incidence, and adverse events) in a cohort of pregnant and breastfeeding women using quantitative and qualitative approaches

- (1) Determine the distribution of women across the PrEP cascade and outcomes including HIV acquisition (maternal and infant) and adverse events
  1. PrEP initiation: defined PrEP start at any time point in the study
  2. PrEP continuation: defined as return to clinic and PrEP refill within 45 days post initiation
  3. PrEP persistence: defined as reporting taking PrEP in  $\geq 5$  out of last 7 days or  $\geq 25$  out of last 30 days (self-reported), or  $\geq 600$  fmol/punch from DBS TDF-DP (objective report)
- (2) Evaluate key predictors of PrEP initiation, continuation and persistence on PrEP including age, substance use, relationship status and partner's serostatus

**AIM 2:** Evaluate patient and provider-level factors associated with the PrEP cascade using quantitative and qualitative approaches

- (1) Evaluate individual-level factors (including risk perception, substance use, sexual activity, and partner/family/community encouragement) associated with PrEP initiation, continuation and persistence on PrEP
- (2) Evaluate pill and study factors (including PrEP-related side effects, time to participate in study, participant-provider communication) associated with PrEP initiation, continuation, and persistence on PrEP
- (3) Evaluate disease factors (including partner's HIV status, HIV-related stigma) associated with PrEP initiation, continuation, and persistence on PrEP

**AIM 3:** Apply an established mathematical model to simulate the impact of improvement in the PrEP cascade on HIV infections averted (maternal and perinatal)

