### Study measures

**Under Aim 1, we will measure the following primary outcomes in the PrEP cascade defined as PrEP initiation, continuation and persistence over time in the cohort.**

1. **PrEP initiation:** # of women who initiate PrEP over time / total # of women in active cohort = proportion of women who initiate PrEP
2. **PrEP continuation:** # of women on PrEP who return for study visits (do not miss more than 1 visit) / total # of women in active cohort who are prescribed PrEP= proportion of women on PrEP who continue in PrEP study

3. **PrEP persistence:** defined as reporting taking PrEP in  $\geq 5$  out of last 7 days or  $\geq 25$  out of last 30 days (self-reported), or  $\geq 600$  fmol/punch (~7 doses/week) from DBS TDF-DP at 3rd trimester, delivery and 6 weeks postpartum (objective report)

**In addition we will measure secondary outcomes defined as continuation and persistence during periods of sexual risk.** Different levels of PrEP continuation and persistence may be needed depending on sexual risk. Our study will measure both perfect persistence (e.g. level of objective persistence throughout pregnancy and breastfeeding periods) as well as “prevention-effective” persistence among participants. We will measure persistence through objective and subjective measures to evaluate the agreement between the two measures, and the level of under- or over-reporting.

- a. **Use of PrEP will be measured via:** (i) quarterly testing of DBS to test for TDF-DP adapted from previous studies of PrEP objective measures; (ii) self-reported items that we have adapted from previous studies (including 7-day, 30-day and last visit recall questionnaires), (iii) pill counts and (iv) pharmacy refill records.
- b. **Measurement of prevention-effective execution:** Execution refers to PrEP persistence during a time when at-risk sex happens. It is calculated by: number of doses reported or recorded/number of expected doses based on HIV risk and PrEP initiation/discontinuation.
- c. **Prevention-effective continuation:** Prevention-effective continuation describes the duration of PrEP use during periods of HIV risk and references the absolute time of use during pregnancy and breastfeeding periods. We will adapt the methodology from previous PrEP studies including FEM-PrEP in SA to create a semi-ordinal composite persistence score measuring plasma TDF-DP from blood specimens collected from DBS every 3-months.

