#### **Methods/Approach:**

- (1) **Primary outcome:** See **Table 1** for precise definitions of (1) PrEP initiation, (2) PrEP continuation, (3) PrEP persistence-subjective, and (4) PrEP persistence-objective
- (2) **Primary analysis:** Describe each outcome listed above via cumulative incidences at fixed intervals (e.g., cumulative PrEP initiation by delivery) and incidence densities over time. The general statistical approaches to these outcomes are analogous; data will be described graphically, including product-limit graphs, with preliminary analyses based on standard approaches for rates and proportions.
  - a. **PrEP initiation** will be modelled using a probit model (preferred to estimate risk factors for common outcomes) with individual-level covariates as fixed effects.
  - b. **PrEP continuation** will be examined using similar approaches; in addition, we will use time-to-event methods to estimate factors associated with time to loss (non-continuation) among women having initiated PrEP.
  - c. **PrEP persistence** will be modelled using mixed effects probit models as above and generalized estimating equations to examine the marginal effect of individual-level covariates on persistence during the study.
    - a. **Sub-group analysis:** we will analyze the primary outcomes by sub-groups including age (<25 and  $\geq$ 25 years), STI diagnosis, relationship status, pregnant/postpartum

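### The SAP's template for predictors of PrEP uptake splits person-time by PrEP use and reports undefined hazard ratios, contradicting the SAP's per-woman definition and probit model of initiation

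*Combined protocol and SAP*

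**What the plan says.** The template is Table 1 in SAP Section 4 (Table and Figure Templates), titled "HIV risk factors associated with PrEP uptake in HIV-uninfected pregnant women". Its two column groups are "Person time on PrEP (n=x" and "Person time not on PrEP (n=y", each with n and % sub-columns, followed by crude and adjusted hazard ratios. It is the only template that gives effect estimates for uptake. The baseline table may be split by PrEP status but carries no effect measure.

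The rest of the SAP treats initiation differently:

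- **Definition** (objectives, Aim 1): "PrEP initiation: defined PrEP start at any time point in the study".
- **Measure** (Study measures, repeated in the outcomes Table 1): number "of women who initiate PrEP over time / total # of women in active cohort", a proportion of women.
- **Stopping and restarting** (Statistical analysis considerations for Aims 1 & 2): initiation rests on a woman's "uptake of PrEP and allow for stoppage and re-initiation".
- **Model** (Section 2.4): initiation "will be modelled using a probit model (preferred to estimate risk factors for common outcomes".
- **Effect measure** (Sample size considerations; Section 2.4, Interpretation): relative risks at two-sided alpha 0.05.
- **Time-to-event modelling** (Section 2.4): assigned to continuation, where "we will use time-to-event methods to estimate factors associated with time to loss (non-continuation) among women having initiated PrEP".

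Continuation and persistence are separate primary outcomes with their own template, Table 2 in Section 4.

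**The concern.** A table of uptake predictors should compare women who started PrEP with women who did not, or relate covariates to the rate of starting. This one divides follow-up time by current PrEP use. That quantity is uptake multiplied by time on drug, so the first step of the cascade is mixed with the later ones. One woman can also contribute to both columns:

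- a woman who starts late adds off-PrEP time before she starts (the protocol's follow-up steps offer PrEP again at later visits);
- a woman who stops adds off-PrEP time afterwards, although she did take PrEP up.

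Read literally, a factor that only prolongs use would look like a predictor of uptake, and one that raises both uptake and early stopping could look neutral. The hazard ratio columns do not settle the matter, because nothing says what they estimate. A programmer would have to fill the headers as written or devise an unspecified model for a primary outcome.

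**Working it through.** **Inputs from the SAP.** 1200 women; 60% initiate; about 75% of initiators continue at 12 months; 70% of those adhere; mean follow-up 18 months. The cascade counts reproduce: 1200 × 0.60 = 720; 720 × 0.75 = 540; 540 × 0.70 = 378. No numerical result stands behind the template itself.

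**Assumption.** Mean months on PrEP by covariate group is not in the documents. The values below are illustrative and shown over a range. Starts are taken to be at baseline.

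**Formula.** Share of a group's person-time on PrEP = P(initiate) × mean months on PrEP among initiators ÷ 18.

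**1. Equal uptake, different duration** (uptake risk ratio 0.60/0.60 = 1.0 throughout)

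| Months on PrEP, group A vs B | Share A | Share B | Ratio of shares |
|---|---|---|---|
| 13.5 vs 13.5 | 0.60 × 13.5/18 = 0.45 | 0.45 | 1.0 |
| 13.5 vs 9 | 0.45 | 0.60 × 9/18 = 0.30 | 1.5 |
| 12 vs 6 | 0.60 × 12/18 = 0.40 | 0.60 × 6/18 = 0.20 | 2.0 |

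**2. Different uptake, offsetting duration** (70% vs 50%, uptake risk ratio 1.40)

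- 9 vs 12.6 months: 0.70 × 9/18 = 0.35 and 0.50 × 12.6/18 = 0.35; ratio 1.00, so the difference disappears.
- 6.75 vs 13.5 months: 0.2625 and 0.375; ratio 0.70, so the direction reverses.

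**3. Who fills the off-PrEP column.** With 720 initiators and 480 never-initiators, never-initiators supply 480 × 18 = 8640 woman-months. Initiators supply 720 × (18 − mean months on PrEP):

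- mean 13.5 months: 3240, or 3240/11880 = 27% of the column;
- mean 9 months: 6480, or 6480/15120 = 43%;
- mean 6 months: 8640, or 8640/17280 = 50%.

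**4. Can the hazard ratio be inferred from the text?** A probit model does not yield one. The time-to-event modelling in Section 2.4 starts after initiation. A model of time to first initiation would stop counting a woman's time at her first start, so it would have no on-PrEP person-time group. The incidence densities planned for Aim 1 do not explain the headers either, because a density of first initiation uses only time before the start.

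**The case against.** The strongest reply is that the controlling text is sound. Section 2.4 refers the reader to the outcomes Table 1 for definitions, where initiation is a proportion of women, and it names the probit model. Continuation is analysed separately. Section 4 says that tables for the paper will be built separately. The shell also looks mislabelled: n and % sub-columns and a median-age row suit counts of women, and there is no person-years or rate column. All of this stands, and it limits the point to the template. It does not remove it, because Section 4 also says that its templates cover all analyses.

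A reader might infer that the planned analysis of uptake is biased, or that the reported hazard ratios would be wrong by a factor such as 2.0. The documents do not support that. The 1.5 and 2.0 are ratios of person-time shares under assumed durations. A hazard ratio for time to first initiation would not contain duration at all. Nor should 2.0 be set against the relative risk of 2.0 in the sample-size statement, which is a different measure.

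The durations can also be challenged. A group mean of 6 months sits uneasily with about 75% continuing at 12 months. If the title restricts the table to pregnancy, antenatal time is about 18 − 12 = 6 months, and 12 months on PrEP could not occur. The mechanism does not depend on these values: with equal uptake the ratio of shares equals the ratio of durations, so 4.5 versus 3 of 6 months still gives (0.60 × 4.5/6)/(0.60 × 3/6) = 0.45/0.30 = 1.5.

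Finally, it would be too strict to say that an uptake hazard ratio must use only time before initiation. That holds for first initiation. The SAP allows re-initiation, and in a recurrent-event model time after stopping is properly at risk.

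**Conclusion.** The inconsistency is real and needs no assumed numbers: the definition counts women, the model is probit, the named effect measure is relative risk, and the template shows person-time with a hazard ratio that is defined nowhere. As a further consequence, columns filled in as headed would mix uptake with duration. The ratio of person-time shares would be 1.5 to 2.0 at an uptake risk ratio of 1.0 in the two unequal-duration examples, and a true uptake difference could be hidden or reversed in others. Those sizes rest on assumed group durations, baseline starts and 18 months of follow-up. The finding concerns the table template and the missing specification of its effect measure. The probit analysis of initiation stands. The headers may be a drafting slip, but they should be corrected before the table is programmed.

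**What to change.** - Head the columns with women who initiated and women who did not initiate PrEP by a stated time point, such as delivery.
- Report an effect measure that matches the planned analysis, for example risk ratios. Since the model is probit, state how they are obtained, such as from standardised predicted probabilities.
- If a hazard ratio is kept, define it in the SAP text as time from enrolment to first initiation with only pre-initiation time at risk. If re-initiation is to count, specify a recurrent-event model and its risk set.
- Move person-time on PrEP to the continuation and persistence template (Table 2 in Section 4).

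The cost is a revised table shell, a few sentences in the SAP and the matching programming. No new data are needed.
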